5.3 Subject Re-enrollment

Subjects who screen fail from the study prior to randomization and study drug administration may be re-screened and re-enrolled as long as the subject was not screen failed due to noncompliance with the protocol (i.e., positive urine drugs of abuse screen, etc.). The Medical Monitor must be consulted prior to re-screening any subject. If the subject is re-screened, the subject must be re-consented and the same subject number must be used.

Screen failure data (date of consent, demographics, reason for screen failure, and adverse events, if applicable) will be recorded in the eCRF.

5.4 Subject Withdrawal

Subjects are free to discontinue the study at any time, for any reason, and without prejudice to further treatment. The investigator may remove a subject if, in the investigator's judgment, continued participation would pose unacceptable risk to the subject or to the integrity of the study data. All procedures for early termination must be completed. Reasons for removal or withdrawal may include:

- Withdrawal of consent
- Administrative decision by the investigator or sponsor
- Ineligibility
- Significant protocol deviation
- Subject noncompliance
- Safety concern by the investigator or sponsor

CONFIDENTIAL

- Lost to follow-up

Subjects who are withdrawn prior to completing all study visits may be replaced.

In the event of a subject's withdrawal, the investigator will promptly notify the sponsor and medical monitor and will make every effort to complete the EOS assessments. All withdrawn subjects with ongoing clinically significant clinical or laboratory findings will be followed until the finding is resolved or medically stable; reasonable attempts will be made to follow-up with subjects.

5.5 Early Termination of Study

The study may be terminated at any time by the sponsor if serious side effects occur, if potential risks to study participants are identified, if the investigator does not adhere to the protocol, or if, in the sponsor's judgment, there are no further benefits to be achieved from the study. In the event that the clinical development of the study drug is discontinued, the sponsor shall inform all investigators/institutions and regulatory authorities.

6 TREATMENT OF SUBJECTS

6.1 Identity of Study Drugs

A description of the study drugs is presented in Table 6.1.

Table 6.1 Study Drugs

| Treatment Group and Number of Subjects | Treatment |
|--|--|
| IVR Dose 1 (n=10) | 28-day IVR 80/4 (estradiol 80 µg/day + progesterone 4 mg/day) |
| IVR Dose 2 (n=10) | 28-day IVR160/8 (estradiol 160 µg/day + progesterone 8 mg/day) |
| Oral Reference (n=10) | Oral Estrace/Prometrium QD for 29 days (Estradiol 1 mg/progesterone 100 mg oral capsule) |

DARE-HRT1 IVRs will be sourced by Daré Bioscience Australia Pty LTD; oral Estrace/Prometrium will be sourced by the CRU.

6.2 Treatments Administered

Each subject will receive either an IVR or daily oral capsule for 28 days.

The IVR is self-inserted by the subject and is to remain intravaginal for 28 days, with removal of IVR in the CRU on the morning of Day 29. If a subject cannot self-insert the IVR, the site physician will insert the IVR.

Those enrolled in the oral arm (Estrace/Prometrium) will also begin dosing on Day 1, with a last dose on Day 29. Subjects enrolled in the oral arm will be directed to self-administer the medication in the morning with a meal and approximately 240 mL of water, starting on Day 2 through Day 27. Doses will be administered in the CRU each of the mornings of Days 1, 28, and 29 with a moderate-fat breakfast.

6.3 Method of Assigning Subjects to Treatment Groups

ICON will prepare the randomization scheme in accordance with its SOPs and the randomization plan, which reflect GCP standards. Refer to Section 9.3 for a description of randomization methods. Eligible subjects will be assigned to a treatment group according to the list of subject randomization assignments.

6.4 Measurements of Treatment Compliance

Treatment compliance of study drug administered by IVR will be confirmed by PK evaluation and subject daily diary. Treatment compliance of study drug administered by oral capsule will be confirmed during periods of subject confinement to the CRU, and Day 1, as IP will be administered by licensed healthcare professionals. Treatment compliance while oral capsule IP is self-administered will be confirmed by subject daily diary. Details regarding dosing, including the dose administered and the date and time of dosing, will be recorded. Additionally, meal

CONFIDENTIAL

compliance will be confirmed during periods of subject confinement to the CRU (% of meal completed, etc. will be recorded).

6.5 Investigational Product Storage, Accountability, and Retention

6.5.1 Storage Conditions

The IP is to be stored at refrigerated temperature (2°C to 8°C). The product does not need protection from light. Additional information can be found in the Investigator's Brochure.

The investigator will ensure that all the study drugs are stored and dispensed in accordance with local regulations concerning the storage and administration of investigational drugs.

6.5.2 Drug Accountability and Retention

The investigator must ensure that all study drug supplies are kept in a secure locked area with access limited to those authorized by the investigator. The investigator must maintain accurate records of the receipt of all study drug shipped by Daré Bioscience Australia Pty LTD or their representative, including but not limited to the date received, lot number, expiration date, amount received, and the disposition of all study drug. Current dispensing records will also be maintained including the date and amount of study drug dispensed and the subject receiving the drug. All remaining study drug not required by regulations to be held by the CRU must be returned to Daré Bioscience Australia Pty LTD or their representative immediately after the study is completed.

It is the responsibility of Daré Bioscience Australia Pty LTD to ship a sufficient number of dosage units to allow the CRU to maintain an appropriate sampling on-site as per applicable regulatory requirements. Each reserve sample shall consist of a sufficient quantity to permit the local regulatory agency to perform 5 times all of the release tests required in the application or supplemental application.

6.6 Packaging and Labeling

6.6.1 Investigational Product

Details regarding IP packaging, labeling, and use instructions will be provided in the study reference manual.

6.6.2 Blinding of Treatment Assignment

Not applicable. This is an open-label study.

6.7 Concomitant Medications and Procedures and Other Restrictions

6.7.1 Concomitant Medications and Procedures

No concomitant medications and personal lubricants (water-based lubricants are allowed) or any intravaginal product or medications (prescription, OTC, and herbal), with the exception of paracetamol 650 mg/day (not to exceed 2000 mg total in the 7 days prior to administration of the study drugs), or vaccinations may be administered during the study unless they are prescribed by

CONFIDENTIAL

the investigator for treatment of specific clinical events. No concomitant procedures will be performed during the study unless approved by the investigator. All medications (prescription and OTC), vitamin and mineral supplements, and herbs taken during the study will be documented on the concomitant medication eCRF. Information recorded will include: start and stop dates and times, dose and route of administration, and indication. Medications taken for a procedure will also be included, as well as the procedure itself.

6.7.2 Other Restrictions

Subjects will be instructed to adhere to the following restrictions:

- Strenuous activity (as assessed by the investigator) is prohibited from 48 hours prior to admission until final discharge from the CRU.
- Subjects are not permitted to consume alcohol for 3 days prior to admission to the CRU and should refrain from consumption of alcohol until EOS.
- Subjects are not permitted to consume any food and drink from outside of the CRU while residing at the CRU.
- Subjects must comply with the CRU smoking policy, if applicable.
- Subjects are not permitted to participate in any other clinical trial or donate blood or plasma while participating in this clinical trial.

CONFIDENTIAL

7 STUDY ASSESSMENTS AND PROCEDURES

Subjects will undergo study procedures and assessments at time points specified in the schedule of assessments (Table 1.1 and Table 1.2).

7.1 Medical and Surgical History

The investigator or designee will collect a complete medical and surgical history at screening. Medical and surgical history will be collected at CRU admission to determine if any changes have occurred since screening.

7.2 Demographic Characteristics

Demographic characteristics including sex, age, race, and ethnicity will be recorded.

7.3 Physical Measurements

Height (cm) and body weight (kg) without shoes will be recorded.

7.4 Pharmacokinetic Assessments

7.4.1 Drug Concentration Measurements

Plasma PK samples will be collected at time points specified in the PK sampling schedule within the schedule of assessments (Table 1.1 and Table 1.2). Blood sample collection, processing, and shipping details will be outlined in a separate SRM.

Plasma concentrations of estradiol, estrone, and progesterone will be determined at using a validated method.

7.4.2 Pharmacokinetic Parameters

Pharmacokinetic variables will be calculated from the plasma concentration data using noncompartmental methods (Phoenix™ WinNonlin®, Version 6.4 or later; Certara LP, Princeton, New Jersey, USA) and actual sampling times.

The following PK parameters will be determined:

| | |
|-----------|--|
| C_{avg} | Time-weighted average observed plasma concentration over 24 hours (Day 29 PK profile for oral dosing only) |
| C_{ss} | Steady-state concentration (IVR dosing only) |
| C_{max} | Maximum observed plasma concentration |
| C_{tau} | Concentration at the end of the dosing interval (tau) (oral dosing only) |
| t_{max} | The time that C_{max} was observed |

CONFIDENTIAL

| | |
|----------------|---|
| AUC_{0-24} | Area under the plasma concentration-time curve from time 0 to 24 hours; calculated using the linear/log trapezoid rule (oral dosing only) |
| AUC_{D1-D30} | Area under the plasma concentration-time curve from time 0 (Day 1) to the time of the last quantifiable concentration on Day 30; calculated using the linear/log trapezoid rule (IVR dosing only) |
| $t_{1/2,eff}$ | Effective half-life; calculated using AUC_{0-24} on Days 1 and 29 (oral dosing only) |

Baseline correction, using the average of the three predose concentrations on Day 1, may be performed prior to the calculation of PK parameters by noncompartmental methods. C_{max} (and t_{max}) will be computed over each 24-hour PK profile (Days 1 and 29) and, for IVR administration, over the entire 28-day treatment interval. Additional PK parameters may be calculated as appropriate.

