| Time | | | | 0.5, 1, 2, 4, 8, 12, 24, and 48 hours post insertion | | | | | |
| FSH | X | | | | | | | | |
| Serology tests ^e | X | | | | | | | | |
| Drug and alcohol urine screen | X | X | | | | | | | |
| Transvaginal Ultrasound | X | | | | | | | X | |
| Urine dipstick | X | X | | | | | | X (EOS) | |
| Dispense test article(s) | | | X | | | | | | |
| Training on use of IVR | X | | X | | | | | | |
| Usability and Tolerability questionnaire | | | | | | | | X | |
| Insert Vaginal Ring (after predose PK sample) | | | X | | | | | | |
| Confirm vaginal ring placement | | | | X ^f | X | | X | | |
| PK blood samples | X | X | X (-1, -0.5, and 0 hours predose) | X (once) | X (once) | X (once) | X (0, 0.5, 1, 2, 4, 8, and 12 hours postdose) | X (24 hours postdose) | |
| Remove vaginal ring/Return test article(s) | | | | | | | X | | |
| Review of daily diary | | | | X | X | X | X | | |
| Discharge from CRU | | | | X (Day 3) | | | | X | |
| Follow-up Phone Call ^g | | | | | | | | | X |
| Adverse events | | | | AEs collected beginning at IVR placement and in on-going manner, as appropriate | | | | | |

CONFIDENTIAL

Table 1.1 Schedule of Assessments and Procedures - IVR Treatment Arm

| Study Procedure | Screening | Pre-Treatment | | 28-Day Treatment Period | | | | | Follow-Up Phone Call |
|------------------------|--|---------------|---------------|--|------------------------|--------|--------|--------|----------------------|
| | Days -28 to -2 | Day -1 | Day 1 Predose | Days 1, 2, and 3 | Days 8, 11, 15, and 22 | Day 28 | Day 29 | Day 30 | |
| Time | | | | 0.5, 1, 2, 4, 8, 12, 24, and 48 hours post insertion | | | | | |
| Serious adverse events | SAEs collected beginning at ICF signing and in on-going manner | | | | | | | | |
| Prior/conmeds | X | X | X | Conmeds collected in on-going manner, as appropriate | | | | | |

Abbreviations: AE = adverse event; BP = blood pressure; conmed = concomitant medication; CRU = clinical research unit; ECG = electrocardiogram; EOS = end of study; FSH = follicle-stimulating hormone; ID = identification; HRT = hormone replacement therapy; IVR = intravaginal ring; PK = pharmacokinetic; PR = pulse rate; RR = respiration rate; SAE = serious adverse event; temp = temperature.

- a. Subjects who elect to undergo washout of prior HRT will be asked to sign the informed consent prior to the start of that washout. Washout periods of 8 weeks will require that Screening not commence until 28 days prior to Day 1.

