Day 1 is defined as the first day of treatment, i.e., the day the IVR is self-inserted by the subject. The same IVR is to remain intravaginal for 28 days, with removal of IVR in the CRU on the morning of Day 29. For those randomized to the oral arm (Estrace/Prometrium), dosing will also begin on Day 1, concluding with a last dose on Day 29. Subjects in the oral arm will be directed to self-administer the medication in the morning with a meal and approximately 240 mL of water, starting on Day 2 through Day 27. Doses will be administered in the CRU each of the mornings of Day 1 and Days 28 and 29 with a moderate-fat breakfast.

Safety and tolerability assessments will include monitoring of adverse events and concomitant medications, clinical laboratory findings, physical examinations, vital signs, pelvic examinations, completion of a Usability and Tolerability questionnaire, and vaginal pH and cytology. Refer to the Schedule of Assessments for each treatment arm in Table 1.1 and [Table 1.2](#) for specific details.

IVR Treatment Groups:

- A single predose blood draw for estradiol, estrone, and progesterone will be obtained at screening and Day -1, and -1, -0.5, and 0 (immediately prior to insertion of IVR \pm 5 min) hours on Day 1. Plasma samples for estradiol, estrone, and progesterone will then be obtained at 0.5, 1, 2, 4, 8, 12, 24, and 48 hours following administration/insertion. Subjects will then be discharged from the CRU after safety assessments have been completed on Day 3.
- Subjects will return on the morning of Days 8, 11, 15, and 22 for a single blood draw as well as safety assessments.
- Subjects will return to the CRU on Day 28 for a PK blood draw, safety assessments, confirmation of IVR placement, and to begin confinement. On the morning of Day 29 a PK blood sample will be collected. The IVR will then be removed and PK samples will be collected 0.5, 1, 2, 4, 8, 12, and 24 hours post-removal.

Additional details of sampling and safety assessment procedures are presented in the Schedule of Assessments and Procedures - IVR Treatment Arm in Table 1.1.

Oral Treatment Group:

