- A single predose blood draw for estradiol, estrone, and progesterone will be obtained at screening and Day -1, and -1.0, -0.5, and 0.0 hours immediately prior to and at 0.25, 0.5, 1, 2, 4, 6, 8, 10, 12, and 24 hours after the first dose on Day 1. Following the 24-hour PK, subjects will be discharged and instructed to self-administer oral estradiol and progesterone treatments each morning, with food and approximately 240 mL of water, at approximately the same time.

CONFIDENTIAL

- Subjects will return on Days 8, 15, and 22 for a single blood draw as well as safety assessments.
- Subjects will return to the clinic and be admitted on Day 28 to consume their oral dose with breakfast. A PK sample will be collected just prior to the last oral dose on the morning of Day 29, with additional PK sampling performed at 0.25, 0.5, 1, 2, 4, 6, 8, 10, 12, and 24 hours postdose.

Additional details of sampling and safety assessment procedures are presented in the Schedule of Assessments and Procedures - Oral Treatment Arm in Table 1.2.

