9.4 Endpoints

9.4.1 Primary Endpoints

- C_{ss} and C_{max} for estradiol, estrone, and progesterone for each treatment

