9.5 Pharmacokinetic Statistical Analysis

The DARE-HRT1 IVR is the test (investigational) product of interest, with two dose combinations of estradiol and progesterone being assessed. Thus, comparisons of the estrogen and progesterone concentrations will be made for each dose combination as DARE-HRT1 IVR versus oral therapy.

The PK analysis will be performed for each IVR dose and assessed versus the oral reference. Graphics will be provided to allow for visual inspection of the mean and individual subject concentration-time profiles.

The PK parameters C_{avg} , C_{ss} , C_{max} , C_{tau} , t_{max} , AUC_{0-24} , AUC_{D1-D30} , and $t_{1/2, eff}$ will be determined from the plasma concentration-time profiles, where possible. Geometric mean values and coefficients of variation (CV%) will be estimated and reported.

If possible, the dose proportionality for the DARE-HRT1 IVR estradiol and progesterone doses will be assessed.

Other details of the PK analysis will be described in a separate Statistical Analysis Plan.

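### Does a Day 29 C_max in the ring arms, taken mostly after the ring is out, spoil the primary C_max endpoint or its comparison with oral?

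*Combined protocol and SAP*

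**What the plan says.** Section 7.4.2 lists eight PK parameters and limits six of them to one route. C_max and t_max have no such limit, and they "will be computed over each 24-hour PK profile (Days 1 and 29) and, for IVR administration, over the entire 28-day treatment interval". A ring subject therefore has three C_max values per analyte (Day 1, Day 29, 28-day) and an oral subject has two. The section adds that "Additional PK parameters may be calculated as appropriate".

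Day 29 differs by arm in Section 4.1. For the ring arms there is one morning sample, and then "The IVR will then be removed and PK samples will be collected 0.5, 1, 2, 4, 8, 12, and 24 hours post-removal". For the oral arm, "A PK sample will be collected just prior to the last oral dose on the morning of Day 29", and ten samples follow that dose. Table 1.1 labels the ring samples as "X (0, 0.5, 1, 2, 4, 8, and 12 hours postdose" on Day 29 and "X (24 hours postdose" on Day 30, although no dose is given to ring subjects on those days.

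Section 9.4.1 makes C_ss and C_max primary "for estradiol, estrone, and progesterone for each treatment". Section 9.5 says "The PK analysis will be performed for each IVR dose and assessed versus the oral reference", without naming a C_max window. Sections 9 and 9.5 leave further analysis detail to a separate statistical analysis plan, whose text is not in the combined document.

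**The concern.** C_max is a primary endpoint in all three arms, whereas the other primary endpoint, C_ss, is defined for the ring only. Of the listed exposure measures, C_max is the only one that carries the same name in the ring and oral arms.

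A reader could therefore expect the Day 29 values to be set side by side. They are different quantities. The oral value is a peak after a dose. The ring value is the highest of eight samples, seven of them drawn after the drug source is gone. A t_max from such a profile would reflect noise and the rate of decline rather than absorption. The label in Table 1.1 makes the misreading easier.

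If the two were compared as like with like, the ring's peak exposure could be understated against oral. With three ring values and none named as primary, the choice could also be made after the data are seen.

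**Working it through.** The protocol gives no figure to reproduce here, so the check has three parts.

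**1. Sample counts (Section 4.1)**

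| Profile | Before removal or dose | After | Total |
|---|---|---|---|
| Ring, Day 29 | 1 | 7 | 8 |
| Oral, Day 29 | 1 | 10 | 11 |

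The share of the ring's Day 29 samples taken after removal is 7/8 = 87.5%. Scheduled ring-in-place samples after insertion are 8 (0.5 to 48 h) + 4 (Days 8, 11, 15, 22) + 1 (Day 28) + 1 (Day 29, pre-removal) = 14. The Day 1 profile and the 28-day window both cover the hours after insertion, so an early ring peak is captured whatever is done with Day 29.

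**2. What the ring's Day 29 C_max measures**

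The documents give no half-life or assay noise for this ring, so both are assumed. The model for the sample at time t after removal is C(t) = C0 × 2^(−t/h) × exp(e). Here C0 is the pre-removal level, h is the half-life, and e is independent normal error with SD = √ln(1 + CV²). At CV 15%, SD = √ln(1.0225) = 0.149. There were 400,000 simulated profiles per setting, at 0, 0.5, 1, 2, 4, 8, 12 and 24 h.

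Geometric mean of the Day 29 maximum divided by C0:

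| Half-life (h) | 1 | 3 | 6 | 12 | 24 |
|---|---|---|---|---|---|
| CV 10% | 1.00 | 1.02 | 1.04 | 1.07 | 1.09 |
| CV 15% | 1.00 | 1.05 | 1.09 | 1.12 | 1.15 |
| CV 30% | 1.05 | 1.17 | 1.25 | 1.31 | 1.37 |

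At CV 15%, the maximum falls on a post-removal sample in 5%, 35%, 52%, 64% and 72% of profiles, and the median t_max is 0, 0, 0.5, 0.5 and 0.5 h. So C_max is close to the end-of-wear level, and t_max carries little information.

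Upward noise is not special to this window. For a flat profile over the 14 ring-in-place samples, the expected maximum of 14 standard normal errors is 1.70. The inflation at CV 15% is then exp(1.70 × 0.149) = 1.29. Moving to the 28-day window would not remove it.

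**3. Whether any stated analysis uses the Day 29 ring value against oral**

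- Section 2.5: no formal hypotheses are tested.
- Section 3.1: the primary objective is to describe ring PK over 28 days, which matches the ring-only 28-day C_max in Section 7.4.2.
- Section 3.2: the comparison with oral concerns systemic exposure over 28 days, for which a single-day peak is not the natural measure.
- Section 9.1: the analyses against oral are descriptive.
- Section 9.5: the comparison is of estrogen and progesterone concentrations, with mean and individual profiles plotted.
- Section 7.4.2: C_ss (ring) and C_avg (oral) also give a pair of sustained-level measures.

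None of these sections pairs Day 29 ring C_max with Day 29 oral C_max.

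**The case for a change.** The case for a change is that the unrestricted Day 29 rule stands in the protocol itself, so a later analysis plan would inherit it. The route limits on six other parameters show that the authors knew how to restrict one. Because Day 29 exists in every arm, same-day pairing is an easy default. The remedy would cost only a few words.

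The reading of the text stands. The rule does reach the ring arms, the two Day 29 values are different quantities, no window is named as primary, and the Table 1.1 label is wrong.

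The predicted harm does not stand. It needs a comparison that no section calls for, made by an analyst who overlooks that the ring came out at the start of the profile. Sections 4.1 and 1 both say so, and Table 1.1 itself shows removal on Day 29. Whether the tables would place the two values under one heading cannot be known from the document. Limiting the rule to oral would remove or rename one descriptive row and leave every other result as it is.

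**Conclusion.** No change to the plan is needed. Followed exactly, it yields a sound Day 1 and 28-day ring C_max, a sound oral C_max, and one extra ring value that describes end-of-wear concentration. That extra value is 1.00 to 1.15 times the pre-removal level at 15% noise, and at most 1.37 times at 30%. These figures rest on the assumed exponential decline, half-lives of 1 to 24 h and independent errors.

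Three small matters remain:

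- **Primary window and pairing.** This is missing detail. The 28-day objective already points to the 28-day ring value, more than one pairing with oral is defensible, and the protocol leaves such detail to the separate analysis plan.
- **The label in Table 1.1.** This is a clerical slip that would not alter when any sample is drawn.
- **The Day 29 ring row.** Dropping or renaming it changes no conclusion of a descriptive study.

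The view would change if the separate analysis plan set the Day 29 ring C_max against the Day 29 oral C_max as equivalent measures.
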